4.1.1 Intervention delivery

Appointments for the participants and follow-up physiotherapy appointments will be managed through the normal service channels at the participating sites, including arrangements for participants who do not attend appointments (DNAs) for treatments.

4.2 Study Training

Clinicians responsible for confirming potentially eligible patients (surgeons and physiotherapists, where appropriate), clinicians responsible for delivering study-related treatments, and research health care practitioners (RHCP) will be trained at each of the participating sites in relation to the participant eligibility criteria, approach to recruitment and consent, completion of all study paperwork requirements, Good Clinical Practice (GCP) as applicable to research and the maintenance of the study site file and study records. Reporting of serious adverse events and adverse events will also be covered.

In addition, the clinical physiotherapists who deliver the physiotherapist-led exercise intervention will be trained prior to the start of recruitment and treatment. The focus of this training will be on individualised exercise prescription and progression and will be supplemented by a comprehensive manual providing clear guidance. This training will also cover study processes, including adverse event reporting. The training will take the form of a workshop consisting of information provision and practical application of the exercise intervention.

For pragmatic reasons relating to limited workforce capacity, the same clinical physiotherapists might treat participants in both groups. However, given the protocolised nature of post-operative rehabilitation, we do not anticipate any problems or expect a significant contamination effect but details of the exercise/rehabilitation programmes delivered in both treatment arms will be recorded on case report forms, as described, and compared.

5 STUDY SETTING

Patients will be recruited from orthopaedic departments of the participating NHS hospitals. The study interventions will be delivered through their associated orthopaedic and physiotherapy services.

6 ELIGIBILITY CRITERIA

6.1 Inclusion criteria

- 1) Adult patients (≥ 18 years)
- 2) Diagnosed with a symptomatic tear of the rotator cuff following a traumatic incident thought to be of sufficient force to induce a tear.
- 3) Rotator cuff tear confirmed by diagnostic ultrasound or MRI scan undertaken as part of routine diagnostic work-up
- 4) Eligible for rotator cuff repair surgery or a programme of physiotherapist-led exercise as determined by the attending clinician (surgeon or physiotherapist, where appropriate)
- 5) Able to return to the participating NHS hospital or associated orthopaedic and physiotherapy services (where physiotherapists have been trained in trial interventions) for post-operative rehabilitation or the programme of physiotherapist-led exercise.

6) Able to understand English.

6.2 Exclusion criteria

- 1) Not eligible for rotator cuff repair surgery or a programme of physiotherapist-led exercise as determined by the attending clinician (surgeon or physiotherapist, where appropriate)
- 2) Patients who are unable to give full informed consent.

7 STUDY PROCEDURES

7.1 Patient identification and recruitment

Potential participants will be identified at the point when the diagnosis of symptomatic traumatic rotator cuff tear is made (sudden onset of shoulder pain and weakness following a traumatic incident with a tear confirmed by ultrasound or MRI) and surgery is considered as a treatment option. The pathway to this point in the care pathway is variable between sites but, typically, this diagnosis and treatment offer will be made by an orthopaedic surgeon, or physiotherapist where appropriate, who will subsequently introduce the trial to the patient. If the patient expresses interest, further discussion will ensue between the patient and the clinician or RHCP (depending on availability) who will provide them with a study information pack, by hand or in the post, and follow this up with a discussion, face-to-face or over the telephone. Building on a successful six-step model to promote recruitment to RCTs that resulted in 57% recruitment of eligible patients in the orthopaedic setting [31], this discussion will include: (1) an explanation of the condition, (2) reassurance about receiving treatment, (3) establishment of uncertainty as to the optimum treatment, (4) an explanation of the study purpose, (5) a balanced view of the two interventions and (6) an explanation of study procedures.

7.2 Consent

Interested and eligible patients will be required to provide written informed consent before participating (see reference below to optional Quintet Recruitment Intervention (QRI) and optional six month qualitative interviews). Typically, written informed consent will be sought at the time of attendance at the orthopaedic clinic or other convenient time prior to the surgery if the patient requests more time to consider participation in the trial. A clinician or RHCP, who will have received appropriate training and is authorised on the trial delegation log, will obtain informed consent. A record of the consent process and a copy of the consent form will be kept in the patients' medical records. The original consent form will be retained in the Study Site File and a copy will be given to the participant. A copy will also be sent to Keele CTU for monitoring purposes. Participants in the SPeEDy RCT have the right to withdraw from treatment and/ or completion of outcome measures at any time without any consequence to any future care they receive. The GP of each trial participant will be sent a letter to confirm that their patient is taking part in the research study.

On receipt of written informed consent, the baseline questionnaire will be completed prior to randomisation. The participant will then access the interventions as per usual treatment pathways, including being placed

on a waiting list for surgery or physiotherapy. Time to intervention will be variable between treatment arms and between treatment sites and will be recorded and reported accordingly, including the proportion of participants who have not commenced their allocated treatment at the three and six month follow-up time points. Should this pilot and feasibility trial prove feasible, the statistical analysis plan for any future main trial will not control for this variation but it will be accounted for, as a co-variate. The current median wait for surgery in the NHS is 74 days and between 14 to 42 days for physiotherapy.

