7.3 The randomisation scheme

Participants will be allocated on a 1:1 ratio, stratified by tear size (large tear $\geq 3\text{cm}$ / small to medium sized tear $< 3\text{cm}$ / or not known), using mixed blocks randomisation. Tear size is usually obtained as part of usual diagnostic work-up prior to confirming eligibility but where this is not known, for whatever reason, this will not preclude randomisation. Randomisation will be undertaken remotely using web-based randomisation to ensure allocation concealment provided by Derby CTU.

Following confirmation of eligibility, receipt of a correctly completed and signed consent form and completed baseline questionnaire, participants will be randomised to one of the two treatment arms. The randomisation will be performed using random permuted blocks, stratified by tear size (1:1 ratio) to ensure that patients with a similar tear size have an equal chance of receiving either treatment. The participant will be informed of the allocation by the clinician or RHCP and will then access the interventions as per usual treatment pathways, including being placed on a waiting list for surgery or physiotherapy.

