8 STATISTICS AND DATA ANALYSIS

8.1 Sample size calculation

Randomising 76 participants will enable the 1-sided lower 90% confidence limit for the follow up rate to be estimated within about 6% of the anticipated 80% level at six months. Further, a sample size of about 76, allowing for dropout, will be sufficient to allow precise calculation of estimates of standard deviation around the OSS for the main trial [44].

Additionally, with reference to treatment crossover of less than 25% (principal concern relates to those randomised to the physiotherapist-led exercise programme crossing over to surgery), randomising 38

participants to the physiotherapist-led exercise programme enables precise 1-sided upper confidence limits (e.g. around 8% above the desired upper level of around 15% for a 90% upper confidence limit).

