8.3 Data analysis plan

As this is a pilot and feasibility RCT, the main analysis will focus on process outcomes, for example consent rate, retention rate, and follow-up rates. Means and confidence intervals of the OSS will be calculated in order to inform the sample size calculation for the main trial. A detailed data analysis plan will be developed and agreed by the TSC.

At the end of the study, we will review the findings and in discussion with the TSC make a recommendation about proceeding to a future main trial. The following success criteria will be used to decide on whether to proceed to developing a main trial funding application:

- i) Identification of eight recruiting sites during the pilot phase with expressions of interest from at least a further eight sites; this criterion recognises that a future main trial would likely require greater than 400 participants and thus a minimum of 20 sites recruiting over a two-year period
- ii) Recruitment rates: Consent and randomisation of 20% or more of eligible patients
- iii) Treatment cross-over less than 25% at six months in each of the two treatment arms. In a future main trial, if treatment cross-over is less than 50% at 12-months this would suggest that significant financial saving could be made while offering useful data to inform decision-making. Hence, if treatment cross-over is less than 25% at six months, with accepted limitations, this will be regarded as acceptable in the context of the upper limit of longer-term cross-over
- iv) Follow-up rates for the OSS greater than 70% at six months.

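### Does the remark in section 7.2 that a future main trial will treat waiting time as a covariate require a change to this pilot's plan?

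*Combined protocol and SAP*

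**What the plan says.** Section 7.2 (Consent) explains that participants reach treatment through normal NHS waiting lists, that time to intervention will vary by arm and site, and that it will be recorded and reported, "including the proportion of participants who have not commenced their allocated treatment at the three and six month follow-up time points". It then looks ahead to what happens if the pilot succeeds: "the statistical analysis plan for any future main trial will not control for this variation but it will be accounted for, as a co-variate". Expected waits are given next: "The current median wait for surgery in the NHS is 74 days and between 14 to 42 days for physiotherapy".

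Section 7.3 gives the order of events. Participants are told their allocation and "will then access the interventions as per usual treatment pathways, including being placed on a waiting list for surgery or physiotherapy".

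The pilot's contribution to sizing a main trial appears in two places. Section 8.1 says the sample "will be sufficient to allow precise calculation of estimates of standard deviation around the OSS for the main trial". Section 8.3 says "Means and confidence intervals of the OSS will be calculated in order to inform the sample size calculation for the main trial", and adds "A detailed data analysis plan will be developed and agreed by the TSC". Progression criterion (i) in section 8.3 asks for "Identification of eight recruiting sites during the pilot phase with expressions of interest from at least a further eight sites", on the ground that a main trial would probably need more than 400 participants and at least 20 sites.

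**The concern.** Three features invite criticism.

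- **Wording.** To a statistician, controlling for a variable and accounting for it as a covariate are the same act, so the clause seems to deny and promise one thing. It does not say whether the primary comparison or a supplementary analysis is meant.
- **Estimand.** The wait arises after randomisation and is partly a consequence of arm. Conditioning on it would remove part of what allocation to surgery entails. The result would be a contrast at equal waits, not the effect of allocation. That matters for the non-inferiority question in section 3.1. The covariate is also undefined for anyone who never starts the allocated treatment.
- **Sizing.** An OSS standard deviation can size an unadjusted comparison once a margin, error rate and power are set. A comparison adjusted for wait also needs the share of variance in wait explained by arm and the within-arm association between wait and OSS. Sections 8.1 and 8.3 plan neither. If adjustment inflated the required size, the reasoning behind criterion (i) might look too optimistic.

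**Working it through.** **1. Does the pilot's size depend on the wait?** Section 8.1 gives 76 participants, 80% follow-up, a one-sided 90% limit and a distance of about 6%. The half-width is z × √(p(1−p)/n) = 1.2816 × √(0.80 × 0.20/76) = 0.0588, or 5.9 points. For cross-over with 38 in the exercise arm and 15%: 1.2816 × √(0.15 × 0.85/38) = 0.0742, or 7.4 points. A continuity correction of 1/76 makes this 8.7, against the stated figure of around 8. Both figures reproduce, and the wait enters neither. The third justification, precision of the OSS standard deviation, does not use it either.

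**2. Do the pilot's analyses or criteria depend on it?** Sections 8.3.1 and 8.3.2 state that primary and secondary outcome analyses do not apply. Section 8.3 plans process outcomes and OSS means with confidence intervals. Criteria (ii) to (iv) are a recruitment rate, a cross-over rate and a follow-up rate. Criterion (i) is a count of 8 + 8 = 16 sites. That is already below the 20 given as a minimum for the main trial, so it was not calculated from a sample size. Both 400 and 20 are stated as lower bounds, so a larger trial would not contradict them.

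**3. Could adjustment matter to a later trial?** The gap in waits is 74 − 42 = 32 days to 74 − 14 = 60 days. With 1:1 arms, adjustment multiplies the variance of the treatment effect by (1 − q)/(1 − R²). Here R² is the share of variance in wait explained by arm, and q is the share of within-arm OSS variance explained by wait. The documents give no spread of waits and no q, so these are assumptions:

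| Assumed model for wait | Participants equivalent to 400 unadjusted, q = 0 |
|---|---|
| Days, log-normal, medians 74 v 42, log-SD 0.5 / 0.8 (R² 0.199 / 0.073) | 500 / 432 |
| Days, log-normal, medians 74 v 14, log-SD 0.5 / 0.8 (R² 0.528 / 0.261) | 847 / 542 |
| Same inputs, log of wait as covariate | 450 to 1,509 |
| Mean gap 32 days, within-arm SD 60 to 20 days | 429 to 656 |
| Mean gap 60 days, within-arm SD 60 to 20 days | 500 to 1,300 |

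Worked example: a 32-day gap with SD 30 gives 1 + (32/30)²/4 = 1.284, and 400 × 1.284 = 514. With a within-arm correlation of 0.4 (q = 0.16), the last two rows run from 360 to 1,092, so the required size can also fall. Adjustment saves participants whenever q exceeds R².

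**4. Would the estimand move?** Yes, if wait affects OSS. In a simulation with an assumed loss of 0.02 OSS points per day of wait and no other arm effect, the unadjusted differences were −0.66 (32-day gap) and −1.21 (60-day gap). The adjusted differences were about 0.

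**5. Are the needed data available?** Section 7.8 collects the date treatment commenced, and section 7.2 commits to reporting waits. The variance in wait explained by arm, and the association of wait with OSS, can both be calculated from pilot data without new collection.

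**The case for a change.** The strongest argument for a change is that a protocol should not commit a later trial, even loosely, to conditioning on a post-randomisation variable. The cost of deleting or rewording one clause is trivial, and if left it could carry an unclear estimand into the main-trial application. The charitable reading, that waits will not be standardised by design but will be modelled, does not fully rescue the text: its subject is the analysis plan, and it still makes wait a covariate.

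The statistical part of this stands. Wait should not enter the main as-randomised comparison unnoticed, and the clause is badly worded. The consequences claimed for it do not stand. Section 8.3 says the OSS figures inform the sample size, not that they settle it. No margin, error rate or power is given, so no standard deviation could settle it. The site-count argument treats lower bounds as point values. The inflated sample sizes depend on assumed spreads, and on taking 14 or 42 days as the median of a whole arm when section 7.2 may be giving a range of waits.

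The coding gap is also smaller than it looks. Under the log-normal assumption 34% to 40% of the surgery arm would be unstarted at 91 days, but 3.5% to 13% at 183 days and 0.1% to 2.3% at 365 days. Participants who cross over and never start their allocated treatment would still need a rule, but only in an analysis that uses wait.

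**Conclusion.** No change to the plan follows. The clause is loosely worded and, on one reading, describes an adjustment that would no longer estimate the effect of allocation. It is a forward-looking remark about a trial that may never be run. Deleting it would alter no pilot estimate, no progression criterion and not the sample size of 76. The descriptive reporting of waits promised in section 7.2 is sound as it stands.

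The missing details are the analysis that would use wait, its association with OSS, and the coding of participants who have not started. They belong in the main trial's analysis plan. If wanted sooner, they can be covered in the detailed pilot analysis plan still to be agreed by the TSC. A statistician writing either would be expected to keep the as-randomised comparison free of a post-allocation covariate and to treat wait as descriptive or supplementary.

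The conclusion that the pilot is unaffected rests on the text of sections 7.2 and 8.1 to 8.3 and needs no assumption. The possible effect on a later trial's size does rest on assumptions. It runs from a modest saving to more than a threefold increase, and so supports no particular figure.

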7.3 The randomisation scheme

Participants will be allocated on a 1:1 ratio, stratified by tear size (large tear $\geq 3\text{cm}$ / small to medium sized tear $< 3\text{cm}$ / or not known), using mixed blocks randomisation. Tear size is usually obtained as part of usual diagnostic work-up prior to confirming eligibility but where this is not known, for whatever reason, this will not preclude randomisation. Randomisation will be undertaken remotely using web-based randomisation to ensure allocation concealment provided by Derby CTU.

Following confirmation of eligibility, receipt of a correctly completed and signed consent form and completed baseline questionnaire, participants will be randomised to one of the two treatment arms. The randomisation will be performed using random permuted blocks, stratified by tear size (1:1 ratio) to ensure that patients with a similar tear size have an equal chance of receiving either treatment. The participant will be informed of the allocation by the clinician or RHCP and will then access the interventions as per usual treatment pathways, including being placed on a waiting list for surgery or physiotherapy.

7.4 Blinding

No measures to blind participants, clinicians, research team or oversight committees will be implemented in this external pilot and feasibility RCT.

7.5 Unblinding

Not applicable.

7.6 Baseline data

To meet the pre-specified objectives, the following baseline data will be collected:

Measure	Description
Patient descriptors	
Demographics	Gender, date of birth, height, weight
Duration of shoulder pain	Patient self-report in months: 1 question
Smoking status	Patient self-report: 1 question (current tobacco smoker/ past tobacco smoker / current e-cigarette vaper / past e-cigarette vaper/ never smoked or vaped)
Diabetes	Patient self-report: Yes/ No
Employment	Patient self-report: Current employment status : 1 question
Preference for treatment intervention	Patient self-report: 1 question with 3 options
Clinical status	
Shoulder Pain (Patient self-report)	Oxford Shoulder Score (OSS); 12 items, 5 discrete responses per item
Shoulder Function (Patient self-report)	Oxford Shoulder Score (OSS); 12 items, 5 discrete responses per item
Health related quality of life (Patient self-report)	EuroQol: EQ-5D-5L
Diagnosis	
Size & location of rotator cuff tear	Size according to imaging (USS or MRI): 1 question with 5 options (small <1cm, medium ≥1 but <3cm, large ≥3 but <5cm, massive ≥5cm, not known). Location according to imaging (USS or MRI): 1 question with 5 options – more than one can apply (supraspinatus, infraspinatus, subscapularis, teres minor, not known)

Consenting patients will complete the baseline questionnaire, including demographic data and GP details, the Oxford Shoulder Score (OSS), and EQ-5D. The participant will be given adequate time and a suitable location to complete the baseline questionnaire. It will be checked for completeness before proceeding to randomisation. The original baseline questionnaire will be returned to Keele CTU and a copy retained in the Study Site File. Once the baseline questionnaire is completed and checked the participant will be randomised to either the intervention or comparator.

The OSS is a 12-item shoulder-specific self-report measure of shoulder pain and function primarily for the assessment of outcome of shoulder surgery in RCTs [32]. The OSS is reliable, valid, responsive and acceptable to patients [1,32,33]. The items refer to the past 4 weeks with five ordinal response options scored from 0 to 4, with 4 representing the best outcome. When the 12 items are summed, this produces an overall score ranging from 0 to 48, with 48 being the best outcome.

The EQ-5D-5L is a generic measure of health related quality of life that provides a single index value for health status that can be used for the purpose of clinical and health economic evaluation [34]. The EQ-5D-5L consists of questions relating to five health domains (mobility, self-care, usual activities, pain/discomfort, anxiety/depression) and respondents rate their degree of impairment using five

response levels (no problems, slight problems, moderate problems, severe problems and extreme problems) [34]. EQ-5D is the National Institute for Health & Care Excellence's (NICE) preferred measure of health-related quality of life in adults.

7.7 Trial assessments

To meet the pre-specified objectives, the following data will be collected:

Assessment	Description
Feasibility of recruiting patients	Numbers of patients screened, number eligible, number approached, number consenting, number randomised, and number accepting allocation
Retention and follow-up rates	Numbers of participants continuing in allocated treatment Follow-up response rates to questionnaires at three and six months post-randomisation (including Oxford Shoulder Score and EQ-5D-5L)
Zone of clinical equipoise	Data from screening logs, including reasons for not approaching potentially eligible patients Qualitative data; audio recording and individual interviews
Proportion and reasons for treatment cross-over	Numbers of participants receiving treatment (surgery or PT-led exercise) other than that which was allocated to determine proportion of participants who cross-over Qualitative data; individual interviews
Number of potential and willing sites for the future main trial.	Number of recruiting participating sites and numbers of additional sites who are interested in participating in the main trial
Barriers and facilitators to recruitment and retention	Data from screening logs Qualitative data; audio recording and individual interviews
Patient participant satisfaction with the interventions	Participant satisfaction with intervention using a questionnaire with 5-point ordinal satisfaction question

